7.2. Baseline and Pre-Procedure

Subject preparation will occur in accordance with standard hospital policy for the care of interventional cardiology or CABG subjects.

7.2.1. Demographics and Medical History

In all study subjects (randomized or registry), demographics and medical history will be captured in the eCRF.

7.2.2. Pre-PCI Medication

Aspirin. Preloading with aspirin 300 to 325 mg at least 2 hrs before the PCI is mandatory. For subjects already receiving chronic aspirin therapy, the loading dose of 300 to 325 mg of aspirin must still be given. Either chewable or intravenous aspirin is mandatory for the loading dose in subjects not on chronic aspirin who will receive only one dose of aspirin before the ULMCA PCI.

ADP antagonists. ADP antagonist pre-loading therapy is mandatory. In patients undergoing PCI, the ADP antagonist must be given prior to the start of the interventional procedure according to the timing for the selected agent below. For subjects already receiving chronic ADP antagonist therapy, pre-loading is still mandatory. The choice of either clopidogrel, prasugrel or ticagrelor is left to the discretion of the investigator. The one exception where ADP antagonist loading may be first given after the procedure is in the case of the patient who qualifies for randomization except for the presence of a visually estimated 50% - <70% diameter stenosis of the left main in whom IVUS or FFR will be performed for confirmation of lesion severity. In this case, since the patient will be randomized in the catheterization laboratory after IVUS or FFR, ADP antagonist pre-loading is permitted but is not mandatory; if the patient randomizes to PCI, however, and had not been preloaded, ADP antagonist preloading must be administered within 2 hours post PCI. In case of preloading, the following schedule is recommended:

- clopidogrel 600 mg >6 hrs before PCI, or 300 mg >12 hrs before PCI (even if the subject is on chronic ADP antagonist therapy); or
- prasugrel 60 mg >1 hr before PCI (even if the subject is on chronic ADP antagonist therapy); or
- ticagrelor with dosing per labeling >1 hr before PCI (even if the subject is on chronic ADP antagonist therapy) if approved by the local regulatory authorities during the randomization period of this protocol.

Pre-PCI statin therapy. Recent randomized trials^{62, 63,64, 65, 66} have demonstrated that high dose statin therapy decreases PCI-related myonecrosis in subjects undergoing stent implantation, whether or not the subject is already taking chronic statin therapy. Therefore, in the absence of absolute contraindications to statin use (e.g. severe allergy with prior use), it is strongly recommended to give the statins 12 hours in advance (at least one dose), but in all cases at least 1 hour before the PCI, regardless of LDL level and history of prior statin use.

- atorvastatin 80 mg
- rosuvastatin 40 mg

The above statin regimens are required per the protocol. In certain circumstances, sites may not be able to follow the protocol required statin regimen. In these cases, the site must agree to an alternative regimen with the sponsor in writing prior to randomizing any patients. Failure to prospectively document and obtain approval of the alternative therapy will lead to the assessment of a protocol deviation.

Other medications. The use of other medications prior to PCI (e.g. beta-blockers, ACE inhibitors) is left to the discretion of the treating physicians.

7.2.3. Pre-CABG Medication

It is strongly recommended that subjects are treated with aspirin, statins, and antihypertensive medications prior to surgical revascularization. For subjects on clopidogrel, prasugrel, or ticagrelor prior to CABG, these agents should be discontinued and CABG postponed for at least 5 days, 7 days or 5days, respectively, if the subject is stable. Subjects receiving amiodarone prophylaxis should be loaded prior to surgery, and have their treatment continued for a minimum of five days after surgery. It is strongly recommended that ACE inhibitors be stopped sufficiently before surgery to ensure they are no longer effective at the time of surgery.

7.2.4. 12-Lead ECG

12-lead ECGs must be collected only in the randomized cohort, at pre-procedure, within 24 hours post procedure, at discharge, and at one year follow-up. If the one year follow-up is performed through phone contact, the mandatory ECG must be performed at a local institution and submitted to the investigative site. In addition, 12-lead ECG should be recorded during clinical episodes of ischemia or other adverse cardiac event and included in the event source documentation of the subject.

7.2.5. Laboratory Tests

In the randomized cohort, the following lab tests will be required pre-procedure: HbA_{1c}, CK-MB, hemoglobin, WBC, platelet count and serum creatinine, whereas hsCRP and BNP are highly recommended.

Initial screening must show that CK-MB is within normal limits. If the subject has had a recent MI and the troponin level is still >ULN, the CK-MB must have fallen to within normal limits to qualify the subject for randomization. If the CK-MB is still elevated the subject is not eligible for randomization until the CK-MB has fallen to <ULN. Cardiac markers must be measured in all subjects at baseline and twice within 24 hours following the revascularization procedure: at 12 ± 2 hours (i.e. 10-14 hours) and at 24 ± 2 hours (i.e. 22-26 hours) post procedure or at discharge if sooner. In addition, with any significant new clinical episodes of angina or adverse cardiac events, cardiac markers should be repeated and followed for 6-18 hours post ischemia. CK-MB levels must be used to assess baseline entry criteria and post procedure myonecrosis. Either CK-MB or Troponin I or T levels may be used to assess myonecrosis >48 hours post procedure.

Note: Discharge is considered when subject leaves the treating or referral hospital.

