Indeed, the results of SYNTAX, as well as the numerous other trials discussed above suggest equipoise between PCI with first generation DES and CABG for the composite of mortality,

myocardial infarction or stroke, albeit with higher rates of repeat revascularization for PCI.

Although the importance of mortality, MI and stroke as essential endpoints is universally accepted, no single trial has been adequately powered to examine whether CABG has superior, comparable, or non-inferior rates of the composite endpoint of mortality, MI, or stroke compared expressed that the inclusion of unplanned revascularization into the primary SYNTAX endpoint (which was necessitated for sample size requirements) biased the trial against PCI, as many other endpoints of equal or more important impact to patient well-being might have been selected instead. As discussed above, most trials (including SYNTAX) have shown that stroke rates are higher after CABG than PCI, an endpoint significantly more important to physicians and subjects than repeat revascularization. Peri-procedural bleeding is significantly more common after CABG compared to PCI, and is a powerful independent predictor of early and late mortality in this setting.^{38, 39, 40}Subjects undergoing CABG compared to PCI have prolonged hospital stays (for example, mean 3.4 days after PCI vs. 9.5 days after CABG, P<0.001),⁷ greater and prolonged incisional chest pain, and delayed return to work and activities of daily life. The impact of all of these adverse events, including the benefits from the greater prevention of recurrent ischemia and repeat revascularization with CABG compared to PCI, may be captured in quality of life measures. As reported from the One-Year Quality of Life SYNTAX Substudy,⁴¹

PCI as compared to CABG had superior measures of quality of life in most measures at one month, though these outcomes had equalized by 6 and 12 months (Figure 2.5).

Figure 2.5 SYNTAX Trial: Quality of Life Measures Comparing PCI and CABG

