5.2. Other Secondary Endpoints

The primary endpoint composite event rate (all-cause death, MI or stroke) and powered secondary endpoints at all time points other than median of 3 years will be other secondary endpoints.

Time points for all other secondary endpoints, unless specified otherwise, are in-hospital, 30 days, 6 months, 1, 2, 3, 4, and 5 years post-procedure. The other secondary endpoints are:

- All-cause mortality
 - Cardiac death
 - Non-cardiac death
- All MI (peri-procedural, spontaneous, Q-wave and non Q-wave) including large and small MIs
- Protocol-defined MI
- MI adjudicated per Universal MI Definition
- Stroke (all, ischemic, and hemorrhagic)
- Disability following stroke event at 90 days± 2 weeks

- Ischemia-driven revascularization
 - Ischemia-driven target lesion revascularization (TLR)
 - Ischemia-driven target vessel revascularization (TVR)
 - Ischemia-driven non target vessel revascularization (Non-TVR)
- All revascularization (ischemia driven and non-ischemia driven)
 - All target lesion revascularization (TLR)
 - All target vessel revascularization (TVR)
 - All non-target vessel revascularization (non-TVR)
- Complete revascularization at baseline procedure, anatomic and functional (see Section 19. Appendix D).
- Stent thrombosis (ARC definition) symptomatic or asymptomatic
- Symptomatic graft stenosis or occlusion (since this requires angiographic documentation, this endpoint will be compared to symptomatic ARC definite stent thrombosis)
- Bleeding complications
 - Requirement for blood product transfusion
 - TIMI scale (major or minor)
 - BARC scale
- Requirement for blood product transfusion
- Time from randomization to procedure; time from procedure to discharge; ICU days; time from procedure to return to work
- Major adverse events (MAE) defined as composite of the following components. MAE will be assessed in-hospital and at 30 days only.
 - death
 - myocardial infarction
 - stroke
 - Transfusion of ≥ 2 units of blood
 - TIMI major or minor bleeding
 - major arrhythmia
 - unplanned coronary revascularization for ischemia
 - any unplanned surgery or therapeutic radiologic procedure
 - renal failure
 - sternal wound dehiscence
 - infection requiring antibiotics for treatment
 - intubation for >48 hours
 - post-pericardiotomy syndrome.

Definitions of terms and endpoints are located in Sections 16.1 and 16.2. Acronyms and abbreviations are defined in Section 16.0. Other secondary endpoints are included in the QoL sub-study.

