7. TREATMENT OF SUBJECTS

7.1. Schedule of Events – Randomized Trial

	Screening	Pre-procedure / Baseline	Procedure	Post-procedure	visit preferred ¹ 1M \pm 7d	Phone or office visit 6M ± 14d	visit preferred ¹ 1Y (-30d, +60d)	visit preferred ¹ 2Y (-30d, +60d)	visit preferred ¹ 3Y,4Y, 5Y (-30d, +60d)	possible visits 6Y, 7Y, 8Y, 9Y, 10Y (-30d, +60d)
Local Heart Team meeting	x									
Estimate LM disease severity	х									
Angina status	х			х	х	х	х	х	х	х
Eligibility criteria	х									
SYNTAX score	х									
Physical examination	х									
LVEF (echo, MRI or cath)10	х									
Informed consent		х								
FFR / IVUS(if DS ≥50 and <70%) ²		х								
Demographics, Medical History		х								
12 lead ECG		x ³		x ³			x ⁴			
Laboratory tests										
HgbA _{1c} (required), hsCRP & BNP (recommended)		x								
Hgb, WBC, Platelets		х								
CK / CK-MB		x ⁵		x ⁶						
Serum creatinine		х								
mRS assessment		x ⁷			X ⁹	X ⁹	X ⁹	X ⁹	X9	
Stroke Assessment					V 9	×9	V 9	V 9	×9	
(TIA Questionnaire)*					X	X	X	X	X	
Cardiac medication		х	х	х	х	x	х	x	x	х
QoL questionnaire		х			х		х		x ⁸	х
Treatment assignment		х								
Safety assessment & reporting		←(S)AE AND Study event REPORTING								
Event related source docs		←collecting source documents related to events								
CABG / PCI treatment			х							
Document resource utilization				х	х	x	х	x	х	х

1 Office visits are strongly recommended. If that is not possible, phone contact with subject or subject's local physician is acceptable. As a last resort, notification of death by civil registry will be accepted.

2 For an intermediate left main lesion (≥50 - <70% visual DS) without non-invasive evidence of a hemodynamically significant ULMCA lesion; prior to randomization, a cath lab procedure must document left main IVUS ≤6mm² (preferred) or FFR ≤0.80.

- 3 ECGs to be collected for independent core lab assessment at baseline, within 24 hours post procedure (ideally at the same time as the first CK-MB draw), at discharge, and during any adverse cardiac event.
- 4 ECG to be collected for independent core lab assessment at 1Y visit. If the 1Y contact is by phone, the ECG must be done at a local institution and submitted to investigative site.

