7.6.1. Laboratory Assessments

The laboratory assessments need to be obtained according to the Schedule of Events included in Section 7.1.

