See Section 19, Appendix D for the definitions of complete anatomic and ischemic revascularization.

Major Adverse Event (assessed in-hospital and 30 days only)

Composite of death, myocardial infarction, stroke, transfusion of ≥ 2 units of blood, major arrhythmia, unplanned coronary revascularization for ischemia, any unplanned surgery or radiologic procedure, renal failure, sternal wound dehiscence, infection requiring antibiotics for treatment, intubation for >48 hours, or post-pericardiotomy syndrome.

Major Arrhythmia

Ventricular tachycardia or fibrillation requiring cardioversion or countershock; atrial fibrillation lasting >24 hours; bradycardia or conduction system disease requiring a permanent pacemaker.

Myocardial Infarction from Universal Definition

The analysis of RCT data will include the incidence of MI using the Universal Definition¹⁵¹ for each treatment group evaluated descriptively as a secondary endpoint.

The term myocardial infarction should be used when there is evidence of myocardial necrosis in a clinical setting consistent with myocardial ischemia. Under these conditions any one of the following criteria meets the diagnosis for myocardial infarction:

- Detection of rise and/or fall of cardiac biomarkers (preferably troponin) with at least one value above the upper reference limit together with evidence of myocardial ischemia with at least one of the following:
- Symptoms of ischaemia;
- ECG changes indicative of new ischemia (new ST-T changes or new left bundle branch block);
- Development of pathological Q waves in the ECG;
- Imaging evidence of new loss of viable myocardium or new regional wall motion abnormality.
- Sudden, unexpected cardiac death, involving cardiac arrest, often with symptoms suggestive of myocardial ischemia, and accompanied by presumably new ST

elevation, or new LBBB, and/or evidence of fresh thrombus by coronary angiography and/or at autopsy, but death occurring before blood samples could be obtained, or at a time before the appearance of cardiac biomarkers in the blood.

- For percutaneous coronary interventions (PCI) in patients with normal baseline troponin values, elevations of cardiac biomarkers above the URL are indicative of peri-procedural myocardial necrosis. By convention, increases of biomarkers greater than 3 X URL have been designated as defining PCI-related myocardial infarction. A subtype related to a documented stent thrombosis is recognized.

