- For coronary artery bypass grafting (CABG) in patients with normal baseline troponin values, elevations of cardiac biomarkers above the URL are indicative of peri-procedural myocardial necrosis. By convention, increases of biomarkers greater than 5 X URL plus either new pathological Q waves or new LBBB, or angiographically documented new graft or native coronary artery occlusion, or imaging evidence of new loss of viable myocardium have been designated as defining CABG-related myocardial infarction.
- Pathological findings of an acute myocardial infarction.

Renal Failure

Serum creatinine increase by $\geq 1 \text{ mg/dL}$ from baseline or need for dialysis.

Serious Adverse Event

If the adverse event meets any of the criteria below, it is regarded as a serious adverse event (SAE).

• a) Led to a death,

b) Led to a serious deterioration in health that either:

1) Resulted in a life-threatening illness or injury, or

2) Resulted in a permanent impairment of a body structure or a body function, or

3) Required in-patient hospitalization or prolongation of existing hospitalization, or

4) Resulted in medical or surgical intervention to prevent life threatening illness or injury or permanent impairment to a body structure or a body function.

c) Led to fetal distress, fetal death or a congenital abnormality or birth defect.

d) An important medical event that may not result in death, be life-threatening, or require hospitalization but may be considered serious when, based upon appropriate medical judgment, may jeopardize the patient or subject and/or may require intervention to prevent one of the outcomes listed in this definition.

Stent Thrombosis

For this trial, stent thrombosis will be defined as the occurrence of definite or probable stent thrombosis according to the ARC criteria.

1. Stent Thrombosis: Timing

Туре	Timing
Acute stent thrombosis*	0 to 24 hours after stent implantation
Subacute stent thrombosis	>24 hours to 30 days after stent implantation
Late stent thrombosis†	>30 days to 1 year after stent implantation
Very late stent thrombosis†	>1 year after stent implantation

Stent thrombosis will be reported as a cumulative value over time and at the various individual timepoints specified above. Time 0 is defined as the timepoint after the guiding catheter has been removed and the subject has left the catheterization laboratory.

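### TIMI bleeding and renal failure are judged against baseline hemoglobin and creatinine, but neither is scheduled after the procedure, and the MAE composite they feed has two definitions.

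*Protocol*

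**What the plan says.** **Scheduled bloods.** Protocol 7.2.5 lists the pre-procedure tests in randomized patients as HbA1c, "CK-MB, hemoglobin, WBC, platelet count and serum creatinine, whereas hsCRP and BNP are highly recommended". In the Schedule of Events (Protocol 7.1) the rows "Hgb, WBC, Platelets" and "Serum creatinine" each carry one mark, in the baseline column. CK/CK-MB is the only laboratory row also marked post-procedure, with draws at 12 and 24 hours, or at discharge if sooner. Protocol 7.6.1 adds nothing: "The laboratory assessments need to be obtained according to the Schedule of Events included in Section 7.1". No blood test is scheduled at the 30-day contact.

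**Definitions (Protocol 16.2).** TIMI major is intracranial hemorrhage, a hemoglobin fall of at least 5 g/dL or a hematocrit fall of at least 15 points. TIMI minor is a fall of at least 3 g/dL (10 points) with observed blood loss, or at least 4 g/dL (12 points) without. Renal failure is a creatinine increase of at least 1 mg/dL "from baseline or need for dialysis".

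**The composite.** MAE is assessed in hospital and at 30 days. Protocol 5.2, 9.1.3 and SAP 2.3.3 list TIMI major or minor bleeding as a component, and also "any unplanned surgery or therapeutic radiologic procedure". The definition in Protocol 16.2 has no TIMI component and reads "any unplanned surgery or radiologic procedure, renal failure, sternal wound dehiscence".

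**The concern.** A change from baseline needs a second value, and the plan does not secure one in either arm. Whether a silent hemoglobin fall or creatinine rise becomes an endpoint event then depends on local practice, with treatment known to everyone. For MI the protocol guards against exactly this: 16.1.2 insists on one definition for both procedures to avoid ascertainment bias, and the CK-MB times are fixed. Laboratory-defined bleeding and renal failure have no such protection.

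At stake is the between-arm comparison of TIMI bleeding, renal failure and MAE, the measures on which early morbidity after PCI and CABG will be compared. The second problem is simpler: with two MAE definitions in force, one dataset can give two MAE rates.

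**Working it through.** The plan gives no rate, power or sample size for TIMI bleeding, renal failure or MAE, so there is no figure to reproduce. The check sets definitions against scheduled measurements.

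**1. Which events need a scheduled value?**

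| Event | Route | Needs a post-procedure value? |
|---|---|---|
| TIMI major | Hemoglobin/hematocrit fall | Yes |
| TIMI major | Intracranial hemorrhage | No |
| TIMI minor | Hemoglobin/hematocrit fall, with or without observed loss | Yes |
| Renal failure | Creatinine rise | Yes |
| Renal failure | Dialysis | No |
| BARC 3a/3b | Hemoglobin fall, only with overt bleeding | Only to grade a bleed already seen |
| BARC 3a/3b | Transfusion with overt bleeding, tamponade, surgery, vasoactive agents | No |
| BARC 4 | Intracranial bleed, reoperation, transfusion, chest-tube output | No |

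The gap is therefore confined to TIMI bleeding and creatinine-based renal failure, and to MAE through them.

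**2. What happens when no value exists?** SAP 3.4.2 takes all subjects in the population as the denominator for in-hospital event rates. A patient never tested is counted as event-free.

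**3. Opportunity for detection.** Protocol 2.6 cites, from an earlier trial, "mean 3.4 days after PCI vs. 9.5 days after CABG". The ratio is 9.5 / 3.4 = 2.8, so there are more inpatient days after CABG on which a routine test could reveal an event. The documents do not say how often wards draw blood.

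**4. Illustration on assumed inputs.** Suppose both arms have the same true rate r of laboratory-only events, with detection of 90% after CABG and d after PCI. None of these inputs is in the documents. The spurious difference is Δ = r × (0.90 − d). With 950 per arm and a two-sided 0.05 test, the chance of a nominally significant result favouring PCI is Φ[(Δ − 1.96·SE0)/SE1], with SE0 pooled and SE1 unpooled.

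Worked case, r = 5% and d = 60%: observed rates are 3.0% and 4.5%, so Δ = 1.5 points. SE0 = √(2 × 0.0375 × 0.9625/950) = 0.00872 and SE1 = √((0.03 × 0.97 + 0.045 × 0.955)/950) = 0.00871. Then (0.015 − 0.01709)/0.00871 = −0.24, a chance of 0.405.

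| True rate | d = 80% | d = 60% | d = 40% |
|---|---|---|---|
| 2% | 0.2 points; 0.052 | 0.6; 0.188 | 1.0; 0.486 |
| 5% | 0.5; 0.078 | 1.5; 0.405 | 2.5; 0.868 |
| 10% | 1.0; 0.119 | 3.0; 0.700 | 5.0; 0.993 |

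With equal detection the expected difference is zero and the two-sided error stays at 0.05. Across this range the effect runs from negligible to decisive, so the table shows sensitivity and is not an estimate.

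**5. The two MAE lists.** Protocol 5.2, 9.1.3 and SAP 2.3.3 have 13 components; Protocol 16.2 has 12. The missing one is TIMI major/minor bleeding. A hemoglobin fall of 4 g/dL with no observed bleeding and no transfusion is an MAE under the first three and not under 16.2. The laboratory-only bleeds that may be unevenly detected are thus among the events on which the definitions disagree.

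**The case against.** The strongest reply has several parts.

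- **Direction is not shown.** A reader might infer that these events will be found mostly in the CABG arm. The documents do not support that. The stay figures come from an earlier trial and no draw frequency is given. Protocol 7.3.1 expects many staged PCI procedures, with study assessments repeated each time; its examples are ECG and biomarkers, but this could add blood tests in the PCI arm only. Protocol 8.4 also keeps non-cardiac abnormal values out of adverse event reporting unless they are judged clinically significant, need intervention or end participation, so more draws need not mean more events. This stands, although that filter adds investigator judgement in an open-label trial.
- **BARC.** A reader might extend the point to BARC bleeding. That does not hold: hemoglobin falls count only with overt bleeding, and a bleed within 48 hours of CABG must meet type 4, which has no hemoglobin-fall criterion.
- **Consequence.** Lower peri-procedural morbidity with PCI is one reason given for the 4.2-point margin (Protocol 9.1.6.1, SAP 2.6), so a reader might think the margin is undermined. It was agreed beforehand on expectation; this trial's MAE results do not feed back into it. The affected endpoints are unpowered. Protocol 9.1.7.2 calls their p-values descriptive and SAP 3.4.4 and 3.10 urge caution, although SAP 3.4 still assigns them a two-sided 0.05.
- **Adjudication.** Event rules sit in a separate committee manual that is not among these documents. But no committee can adjudicate a value that was never measured.
- **Radiologic procedures.** The missing word *therapeutic* in 16.2 matters little, because the same section limits the term to complications requiring a return to the catheterization laboratory or operating room.

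**Conclusion.** The point holds in limited form. No post-procedure hemoglobin or creatinine is scheduled in either arm, so laboratory-only TIMI bleeding and creatinine-based renal failure, and MAE through them, depend on local testing. Unequal detection in favour of PCI is plausible from the cited stays, but that is an inference from another trial, and the documents fix neither its direction nor its size. The illustrated 0.2 to 5 points rest wholly on assumed rates and detection probabilities.

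Intracranial hemorrhage, dialysis, transfusion, reoperation and BARC bleeding are largely unaffected. The primary endpoint and both powered secondary endpoints are untouched, and nothing here bears on study success.

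The conflict over TIMI bleeding in the MAE definitions is a plain inconsistency and needs no assumption. Three of the four lists agree, so the intended definition is fairly clear.

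**What to change.** 1. In Protocol 7.1, 7.2.5 and 7.6.1, add hemoglobin and serum creatinine to the existing 24 ± 2 hour CK-MB draw (or discharge, if sooner) in both arms.
2. Base the between-arm comparison of laboratory-defined TIMI bleeding and renal failure on that common-time value. Do not use the lowest hemoglobin or highest creatinine before discharge: an extreme over the stay brings back the dependence on length of stay.
3. In SAP 2.3.3, report laboratory-only and clinically overt events separately by arm, with the number of patients per arm who have any post-procedure hemoglobin and creatinine.
4. Make the MAE definition in Protocol 16.2 match 5.2 and SAP 2.3.3: add TIMI major/minor bleeding and the word *therapeutic*.

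If the index procedures are already complete, items 3 and 4 can still be done.

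The cost is two assays at a draw that is already mandated, the matching eCRF fields and one corrected definition. The price in information is that creatinine rises after the common draw do not count in that comparison, and patients discharged before 24 hours contribute an earlier value.

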16.1.2. Definition of Myocardial Infarction

Different criteria for spontaneous and peri-procedural MI will be utilized.

• **Spontaneous MI** (occurring >72 hours after any PCI or CABG)

Detection of rise and/or fall of cardiac biomarkers (CK-MB or troponin) with at least one value

above the upper reference limit (URL)* together with evidence of myocardial ischemia with at least one of the following:

- ECG changes indicative of new ischemia [ST-segment elevation or depression as defined below, in the absence of other causes of ST-segment changes such as left ventricular hypertrophy (LVH) or bundle branch block (BBB)] *or*
- Development of pathological Q waves (≥ 0.04 seconds in duration and ≥ 1 mm in depth) in ≥ 2 contiguous precordial leads or ≥ 2 adjacent limb leads) of the ECG, *or*
- Angiographically documented graft or native coronary artery occlusion or new severe stenosis with thrombosis and/or diminished epicardial flow, *or*
- Imaging evidence of new loss of viable myocardium or new regional wall motion abnormality

*If the upper reference limit (URL) from the respective laboratory performing the assay is not available, then the URL for myocardial necrosis from the laboratory should be used. If the URL or the URL for myocardial necrosis is not available, the MI decision limit for the particular laboratory should be used as the URL. Reference limits from the laboratory performing the assay are preferred over the manufacturer's listed reference limits in an assay's instructions for use.

ST elevation

New ST elevation at the J point in two anatomically contiguous leads with the cut-off points: ≥ 0.2 mV in men (>0.25 mV in men <40 years) or ≥ 0.15 mV in women in leads V2-V3 and/or ≥ 0.1 mV in other leads

ST depression

New horizontal or down-sloping ST depression ≥ 0.05 mV in two contiguous leads.

The above ECG criteria illustrate patterns consistent with myocardial ischemia

• **Procedure-Related Myocardial Infarction** (occurring within 72 hours of either PCI or CABG)

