In the present study it is essential to have an identical definition for MI after both PCI and Furthermore, given that MI represents one CABG to eliminate ascertainment bias. component of the primary composite endpoint of death, stroke or MI, and that death and stroke are devastating complications, only prognostically important MI that has clearly been associated with subsequent mortality will be included in the primary endpoint. In this regard, small levels of cardiac enzyme elevation after PCI reflect the underlying degree of atherosclerosis¹³⁵ and seem to have little or no prognostic significance, ^{136, 137} Large-scale studies in the stent era have shown that peak post-PCI levels of $\geq 8x$ the upper limits of normal ULN or $\geq 10x$ ULN are required before an association with subsequent mortality emerges,¹³⁸ although some studies have suggested that a CPK-MB of CPK-MB \geq 5x ULN may be prognostically important.^{137,139,140} Myocardial infarction may be difficult to diagnosis in the peri-surgical period given an obligate release of cardiac enzymes from all CABG procedures, although post CABG CPK-MB levels of ≥ 5 fold or ≥ 10 fold increased have been shown to be prognostically related to subsequent mortality.^{141,142,143,144} Moreover, cardiac troponin elevations after PCI are of uncertain prognostic importance, in contrast to

spontaneous troponin elevations in subjects with myonecrosis unrelated to revascularization procedures (spontaneous MI), for which numerous studies have shown to be strongly predictive of subsequent mortality.^{140,145,146,147,148,149,150} Thus, in the present study only CK-MB elevations will be used for determination of peri-procedural MI, whereas troponin or CK-MB elevations may be used to diagnose spontaneous MI.

CK-MB levels will be drawn at baseline and at 12 ± 2 hrs and at 24 ± 2 hrs post procedure (or at discharge if this occurs before 24 ± 2 hrs), and more frequently for signs or cardiac symptoms of clinical or hemodynamic instability. 12-lead EKGs will be recorded at baseline, within 24 hours after the procedure (at the same time as the CK-MB draw if possible) and at discharge.

The baseline CK-MB must be normal for subject enrolment in this study. A post procedure MI will be defined as the occurrence within 72 hours after either PCI or CABG of either:

- CK-MB above 10 x URL (*determined on a single measurement), OR
- CK-MB above 5 x URL (*determined on a single measurement), PLUS

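### Protocol Section 7.2.5 accepts troponin in place of CK-MB from 48 h after a procedure, but the endpoint definition of MI accepts only CK-MB until 72 h

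*Protocol*

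**What the plan says.** What counts as an event is settled in one place. Protocol Section 5.2 states: "Definitions of terms and endpoints are located in Sections 16.1 and 16.2". Within Section 16.1.2, MI is divided by time since revascularization. A procedure-related MI is one "occurring within 72 hours of either PCI or CABG", and a spontaneous MI is one "occurring >72 hours after any PCI or CABG". The markers follow the same division. For the first type the rule is strict: "in the present study only CK-MB elevations will be used for determination of peri-procedural MI". For spontaneous MI, by contrast, either troponin or CK-MB is accepted. The operative definition of the procedure-related type begins "A post procedure MI will be defined as the occurrence within 72 hours after either PCI or CABG of either" and offers two routes: CK-MB above 10 x URL, or CK-MB above 5 x URL together with ECG, angiographic or imaging evidence.

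What sites collect is set out in several places.

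- **Section 7.2.5** fixes draws at baseline, 12 ± 2 h and 24 ± 2 h (or at discharge if sooner). It asks for cardiac markers, not named, to be repeated with new clinical episodes, and makes CK-MB compulsory for myonecrosis after the procedure. It then closes with "Either CK-MB or Troponin I or T levels may be used to assess myonecrosis >48 hours post procedure".
- **Schedule of Events (7.1), footnote 5** requires CK/CK-MB for peri-procedural MI and makes troponin optional.
- **Footnote 6** repeats the 12 h and 24 h CK-MB draws, then accepts either troponin or CK-MB as the additional sample for any adverse cardiac event, with no time limit.
- **Section 16.1.2** also carries a collection instruction: CK-MB at the scheduled times "and more frequently for signs or cardiac symptoms of clinical or hemodynamic instability".

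SAP Section 2.3.3 lists protocol-defined MI as an endpoint but gives no marker rule and no 48 h or 72 h cut-off.

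**The concern.** The last sentence of Section 7.2.5 ends the CK-MB requirement 24 h before the endpoint definition does. The scheduled draws stop at 24 ± 2 h, so whether a new event at 48 to 72 h can be classified depends on the sample taken at the time of the event. If that sample is troponin only, the Clinical Events Committee has an event that it cannot place, and no later query can supply a CK-MB that was never drawn.

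MI is a component of the primary endpoint and of both powered secondary endpoints. Section 16.1.2 explains that one MI definition is used for both procedures to avoid ascertainment bias. Letting a site's choice of marker decide whether an event can qualify works against that aim.

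**Working it through.** **Step 1. The rules side by side, by time after PCI or CABG.**

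| Interval | Section 7.2.5, closing rule | Section 16.1.2, what counts | Agree? |
|---|---|---|---|
| 0 to 48 h | CK-MB | CK-MB only | yes |
| >48 to 72 h | CK-MB or troponin | CK-MB only | no |
| >72 h | CK-MB or troponin | CK-MB or troponin | yes |

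Width of the conflict: 72 − 48 = 24 h, which is 24/72 = one third of the procedure-related window. It arises after each PCI or CABG, including a staged PCI, for which Section 7.3.1 applies the same biomarker collection as at baseline.

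**Step 2. An event in the conflicting stretch.** Take a new non-fatal event at 60 h with troponin alone.

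- Procedure-related MI: not met, because both routes need a CK-MB value.
- Spontaneous MI: not met, because 60 h is not beyond 72 h.

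It cannot be a protocol-defined MI. It could still appear under the Universal Definition (Section 16.2), but that is a descriptive secondary endpoint.

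**Step 3. When an endpoint event is really lost.** All of these must hold:

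1. The event is non-fatal, since a death counts in every composite.
2. CK-MB was not drawn for it.
3. No earlier CK-MB, such as the 12 h or 24 h value, had already qualified.
4. The CK-MB, if drawn, would have exceeded 10 x URL, or 5 x URL with the supporting evidence.
5. For the 3-year Kaplan-Meier endpoints, no later death, qualifying stroke or protocol-defined MI occurs by day 1095. If one does, the patient still counts as a failure and only the event time moves (SAP 2.3.1 and 2.3.2 use time to first component event). For the second powered secondary endpoint, a later unplanned revascularization for ischemia also counts the patient.

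**Step 4. Which endpoints the timing touches.** The endpoints run from randomization.

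- Index procedure at the 2-week limit in Section 4.3: 14 d + 3 d = day 17, before day 30. The 30-day endpoint is exposed as well as the 3-year endpoints.
- Staged PCI at the 4-week limit recommended in Section 7.3.1: 14 d + 28 d + 3 d = day 45, after day 30. Only the 3-year endpoints are exposed.

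These dates assume that the protocol's own time limits are kept. They show which endpoints can be affected, not how often. The documents give no count of suspected events at 48 to 72 h, so no change in event rate or power can be computed.

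**The case against.** The strongest reply is that the protocol, read as a whole, already directs CK-MB. The sentence just before the disputed one in Section 7.2.5 makes CK-MB compulsory after the procedure, footnote 5 requires it for peri-procedural MI, and Section 16.1.2 asks for extra CK-MB draws on instability. The disputed sentence only permits troponin.

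This stands in part. A reader might infer that a site in full compliance with the protocol would lose an MI. The documents do not support that: the loss arises when a site follows the one permissive sentence, helped by footnote 6, over the other text. What remains is that Section 7.2.5 is the laboratory section, its closing sentence is the only one there with a time limit for switching marker, and that limit is the wrong one for the endpoint.

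Three further stronger readings are tempting.

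- *The MI endpoint is itself ambiguous.* It is not. Section 5.2 points to 16.1 and 16.2, and 16.1.2 is clear.
- *Every troponin-only event at 48 to 72 h is a lost endpoint MI.* No. Section 16.1.2 deliberately restricts procedure-related MI to large CK-MB rises, so an event below 5 x URL would not count whichever marker was drawn.
- *The gap favors one arm.* The sentence applies equally to PCI and CABG, and nothing in the documents gives a direction.

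The events committee's manual (Section 8.6) is a separate document and not available here. It may contain query rules, but none can recreate an undrawn sample.

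**Conclusion.** The mismatch is certain on the text: 48 h in Section 7.2.5 against 72 h in Section 16.1.2. For that 24 h stretch the protocol lets a site collect a marker that its own endpoint definition does not accept.

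The consequence is narrower. It is limited to new non-fatal events with troponin only, where an unmeasured CK-MB would have passed the 5x or 10x URL criteria and no earlier value had. At 3 years a later component event partly repairs the loss. The number of such events is unknown and probably small, and no direction of bias is claimed. The day 17 and day 45 figures depend on limits that may be exceeded: Section 4.3 foresees delays beyond 2 weeks, and the 4-week staging limit is a recommendation. The correction is worth making because it protects a component of three powered endpoints at little cost.

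**What to change.** Reconcile Section 7.2.5 with the 72 h boundary in Section 16.1.2. For endpoint ascertainment, CK-MB should be collected for any suspected MI within 72 h of PCI (including staged PCI) or CABG, with troponin optional in addition. Reword footnote 6 of the Schedule of Events to match. No endpoint definition, margin or sample size changes.

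This can go out as a site clarification or be carried in the next amendment. An amendment needs documented IRB/EC acknowledgment or approval before it is implemented (Section 11.2.1), across approximately 165 centers, which would be heavy for this point alone. The running cost is one CK-MB assay in each suspected event at 48 to 72 h that would otherwise have had troponin only. These are likely to be few, though the documents give no number.
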